**4.3.        SCREENING ANALYSIS SET**

A screening analysis set will include all participants who signed the ICF and include screen failures who failed up until catheter placement (e.g., considered a screen failure if biopsy at time of catheter placement does not confirm rGBM). This will be the primary population for the disposition tables and listings. Participants in the screening set will be analyzed based on the treatment assigned.

**5.            STATISTICAL METHODS**

Descriptive statistical methods will be used to summarize the data from this study. Unless stated otherwise, the term “descriptive statistics” refers to number of participants (n), mean, median, standard deviation, minimum and maximum for continuous data and frequencies and percentages for categorical data. Survival endpoints will be analyzed with Kaplan-Meier method and summarized with median, twenty-fifth and seventy-fifth percentiles, and 95% confidence intervals (CI), if applicable.

All data collected during the study will be included in data listings. Unless otherwise noted, the data will be sorted first by treatment, participant, and then by date within each participant number.

All summary tables and figures will be presented by summarizing the overall population.

Analyses will be implemented using SAS® 9.4 or higher (SAS Institute, Cary, North Carolina, USA). The International Conference on Harmonization (ICH) numbering convention, i.e., ICH-E3, will be used for all tables and listings. Upon completion, all SAS® programs will be validated by an independent programmer within the staff of the third-party vendor doing the primary analysis. The validation process will be used to confirm that statistically valid methods have been implemented and that all data transformations and calculations are accurate. Checks will be made to ensure accuracy, consistency with this plan, consistency within tables, and consistency between tables and corresponding data listings. All documents will be verified by the lead statistician to ensure accuracy and consistency of analyses.

### **5.1. PARTICIPANT DISPOSITION, DEMOGRAPHIC AND BASELINE CHARACTERISTICS**

Participant disposition will be presented for the screening analysis set. A summary table will be generated for the overall population. The number of participants who were screened, screen failures, and the reason for screen failure will be summarized. Additionally, the number of participants in each analysis population will be summarized. The end of treatment status including reasons for treatment discontinuation, as well as end of study status including reasons for study discontinuation reason will be provided. Similarly, the death status and primary reason for death will be presented. The number of days on study will also be summarized. Participant disposition including analysis population, end of treatment status and reason, end of study status and reason, and death status (including date of death) and reason will be listed.

Demographic data and baseline characteristics including age at informed consent, gender, race, ethnicity, Karnofsky performance status (KPS) at baseline, and baseline height, and weight will be summarized using descriptive statistics. Frequency of KPS scores < 70, 70, 80, 90, and 100 will be summarized for the safety population set. Demographic data and baseline characteristics will be listed.

### **5.2. DISEASE CHARACTERISTICS**

Disease characteristics including GBM type, disease status, description (Unifocal or Multifocal), lesion site and side, surgical pathology diagnosis, histologic grade, and the number of prior progressions will be summarized using the safety set. Disease characteristics will also be listed.

### **5.3. CONCOMITANT MEDICATIONS**

All medication verbatim terms collected will be coded to Anatomical Therapeutic Classification (ATC) and preferred term (PT) using the World Health Organization (WHO) Data Dictionary (DD) Version Sep2020.

Concomitant medications, including bevacizumab and dexamethasone, will be summarized by presenting the number and percentage of participants by PT and ATC, using the safety set. Participants taking the same medication multiple times will only be counted once for that PT or ATC. Each summary will be ordered by descending order of incidence of ATC class and PT within each ATC class.

The number of participants who receive bevacizumab will be tabulated along with the number of doses administered, and dose levels received. Cumulative actual dose will be summarized. A participant's bevacizumab administration record will be included if it occurred after catheter placement and prior to the participant's Week 104, start date of subsequent anticancer therapy, or end of study/last contact date -- whichever occurs first. If a participant has bevacizumab listed as a post-study systemic monotherapy record, these data will be included in the analysis if the start and stop dates occur prior to any other type of subsequent anticancer therapy (eg, lomustine, pembrolizumab, irinotecan, nivolumab, carboplatin, etc.).

The number of participants who receive dexamethasone will be tabulated. The days on dexamethasone, cumulative actual dose, and average daily dose will also be summarized. Exposure will only be calculated from catheter placement to Week 104, start date of subsequent anticancer therapy, or until the participant's end of study/last contact date -- whichever occurs first.

#### **5.4. BRAIN SURGERY, RADIOTHERAPY AND SYSTEMIC THERAPY**

Brain surgery data will be listed. The number and percentage of participants with prior brain surgery will be summarized; data to be included in the summary are type of procedure, histologic diagnosis, Central Nervous System (CNS) site, and CNS side.

The prior and subsequent radiotherapy will be listed. The number and percentage of participants with prior radiotherapy will be summarized; data to be included in the summary are CNS site, radiation therapy type, and total dose delivered. If a participant experiences more than one prior radiotherapy, the worst-case will be used for numerical summaries and all cases will be presented for categorical summaries. A participant will only be included in a single category once.

All verbatim terms collected for both prior and subsequent systemic therapy will be coded to ATC and PT using the WHO-DD Version Sep2020.

The prior and subsequent systemic therapy will be listed. The prior systemic therapy data will be summarized by presenting the number and percentage of participants by PT and ATC and total number of cycles. Participants taking the same medication multiple times will only be counted once for that PT or ATC. Each summary will be ordered by descending order of incidence of ATC class and PT within each ATC class. Additionally, the total number of cycles will be summarized. If a participant experiences more than one prior systemic therapy, the worst-case will be used for numerical summaries and all cases will be presented for categorical summaries. A participant will only be included in a single category once.

## 5.5. TISSUE BIOMARKERS

Tissue biomarker and core biopsy data will be listed. The following information will be summarized:

- EGFR IHC
- EGFRvIII IHC
- MGMT IHC
- MGMT promoter methylation
- IDH1 R132H
- IDH1 molecular diagnostics
- IDH1 mutation type
- IDH2 molecular diagnostics
- IDH2 mutation type
- TERT molecular diagnostics
- TERT mutation type
- PVR IHC

## 5.6. EXPOSURE

The number of participants who received study drug (lerapoltrev and pembrolizumab) and cumulative actual dose received will be summarized. The number of cycles of pembrolizumab administered will be summarized using 0 cycles, 1-5 cycles, > 5 cycles. The relative dose intensity (RDI) of pembrolizumab will be summarized using the percentage of drug a participant received compared to the planned amount of drug received, such that if the RDI is 100% the participant received all the planned doses. To calculate the RDI is (actual cumulative dose / planned cumulative dose) \* 100.

## 5.7. EFFICACY

### 5.7.1. Primary Efficacy Endpoints

The primary efficacy endpoints are ORR and DOR.

#### 5.7.1.1. Statement of Estimand

The **population for the trial** is defined through appropriate inclusion/exclusion criteria (IC/EC) to reflect the targeted participant population for approval. The analysis population is based on the efficacy analysis set.

The **treatment** of interest is lerapoltrev + pembrolizumab.

The **variable** of interest for ORR is the binary response value for a participant. For DOR, the variables of interest are the time from first response to confirmed progression/death/censoring.

The ability to evaluate treatment effect using the variables may be impacted by **intercurrent events** (ICEs). Death and use of additional cancer treatments may all impact the interpretation of treatment effect. For ORR, a composite strategy will be used to address intercurrent events (ICEs)

of potential death and start of additional cancer treatments, meaning occurrence of any of these events prior to a participant achieving CR or PR will mean the participant is considered a non-responder. DOR will use a composite strategy as well, treating death as an event that ends response, and the start of additional cancer treatments medications will be censored under the strategy.

The **population level summary measures** are the ORR, and the Kaplan Meier (KM) estimated median DOR, and associated CI for treatment.

#### **5.7.1.2. Primary Efficacy Analysis**

All efficacy endpoints for participants receiving lerapoltrev and  $\geq 1$  dose of pembrolizumab will be summarized for the overall population.

The number of participants in each category of best overall response (CR, PR, SD, PD), and ORR will be summarized. ORR along with their associated exact 95% two-sided confidence intervals (CIs) using Clopper Pearson method will be computed.

The number of participants with disease progression or death and the number of censored participants will be summarized. DOR will be summarized using Kaplan-Meier methods, and the descriptive statistics of median, 25% and 75% percentiles along with their 95% CIs will be calculated. The Kaplan-Meier survival curve will also be plotted.

Supportive data listings will also be provided.

#### **5.7.2. Secondary Efficacy Endpoints**

The secondary efficacy endpoints for the study are:

- DCR
- OS (including median OS and LS)

#### **5.7.2.1. Secondary Efficacy Analysis**

OS, including LS rates at  $\geq 6$  and  $\geq 12$  months will be summarized using Kaplan-Meier method to estimate the median, 25% and 75% percentiles along with their 95% CIs.

In addition to the quartile summary from Kaplan-Meier method, Kaplan-Meier estimates will be provided for the survival rates at 6 and 12 months along with the 95% CIs for OS.

Analysis of DCR will be conducted in a similar manner to ORR in [Section 5.7.1.2](#).

### **5.8. SAFETY**

Values for all safety variables will be listed by participant and visit (as applicable). Safety summaries by visit will use scheduled visits up to Week 104.

### 5.8.1. Adverse Events

AEs will be mapped to a Medical Dictionary for Regulatory Activities (MedDRA) version 23.1 by system organ class and PT. If a participant experiences multiple events that map to a single PT, the greatest severity and strongest assessment of relation to a study drug will be assigned to the PT for the appropriate summaries. AE severity will be assessed according to the CTCAE version 5. If CTCAE grading does not exist for an AE, the severity of the AE will be graded as mild (1), moderate (2), severe (3), life-threatening (4), or fatal (5).

The number of participants for the following groups will be summarized by overall:

- Any TEAE
- Any TEAE related to a study drug or catheter with sub bullets for TEAEs related to catheter placement, lerapolturev or pembrolizumab
- Any TESAE
- Any TESAE related to a study drug or catheter with sub bullets for TESAEs related to catheter placement, lerapolturev or pembrolizumab
- Any DLTs
- Any AESIs for lerapolturev
- Any irAEs for pembrolizumab
- Any TEAEs leading to discontinuation of study treatment
- Any TEAE with grade  $\geq 3$
- Any TEAE with grade  $\geq 3$  related to study drug or catheter with sub bullets for TEAEs with grade  $\geq 3$  related to catheter placement, lerapolturev or pembrolizumab
- Any Grade 5 TEAEs
- Any Grade 5 TEAEs related to study drug or catheter with sub bullets for Grade 5 TEAEs related to catheter placement, lerapolturev or pembrolizumab

The occurrence of TEAEs and TEAEs related to study drug or catheter will be summarized by PT, system organ class, and severity. All AEs reported will be listed for individual participants showing both verbatim and PT. All AEs that occurred prior to catheter placement will be excluded from the tables but will be included in the listings.

Missing onset dates will be imputed as previously outlined in Section 3.2.3.2 as required to determine TEAEs.

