### 1.2.3 Summary of rGBM Clinical Studies with PVSRIPO

The first-in-human PVSRIPO study (Pro00031169) investigated PVSRIPO delivered via CED in 61 adult patients with rGBM who failed prior SOC therapies (any recurrence; 1 to 5.5 cm contrast-enhancing supratentorial tumor). Dose levels ranging from  $10^7$  up to  $10^{10}$  TCID50 were examined in a dose escalation phase followed by a dose expansion phase, which established the

recommended Phase 2 dose of  $5 \times 10^7$  TCID50 [5]. In the dose-expansion phase (n=31), 19% of patients had a PVSRIPO-related AE of grade 3 or higher. Events most often attributed to PVSRIPO included those related to PTE or CE (eg, headache, pyramidal tract syndrome, seizure, dysphasia) and PVSRIPO was well tolerated systemically.

In the ongoing multicenter Phase 2 study (Pro00077024), as of August 2020, 120 adult rGBM patients with similar inclusion criteria as the Phase 1 study (Pro00031169; limited to 2nd recurrence), have been treated with PVSRIPO at  $5 \times 10^7$  TCID50. Based on a recent safety summary of the ongoing Phase 1 and 2 studies conducted in February of 2020, TEAE with some degree of attribution to PVSRIPO treatment occurring in  $\geq 20\%$  of patients included localized inflammation with nervous system disorders related to PTE (eg, headache, pyramidal tract syndrome, seizure, dysphasia) and fatigue.

Based on an earlier published summary of the 61 patients in the Phase 1 study, the estimated percentage of rGBM patients surviving long-term (ie, landmark survival [LS]) in patients treated with PVSRIPO was 21% at 24 through 60 months [5]. This was favorable when compared to criteria matched external controls and a literature summary. The estimated percentage of patients surviving in the external control group was only 4% at 36 months and 2% at 60 months. In the summary of interventional studies of marketed and investigational agents in rGBM patients reported in the recent literature, the weighted mean estimate of patients surviving at 36 months was 2.71% (9 treatment arms) and 0.56% at 60 months (6 treatment arms) (data on file, Istari).

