## 8 Statistical Analyses

This single-arm study is designed to evaluate the efficacy, safety and tolerability of PVSRIPO when followed by pembrolizumab treatment in patients with rGBM. Summary statistics (eg, n, %, CI) will be employed to describe the key findings (ORR, DOR, incidence and severity of DLT, Grade 3 or higher AE, etc.).

Adverse events considered related to screening or other pre-infusion procedures that are not standard of care (eg, PV booster, biopsy prior to infusion, catheter placement without PVSRIPO infusion) will be summarized separately from TEAE (after PVSRIPO infusion), as will data from patients receiving only PVSRIPO and not at least one dose of pembrolizumab. The number of doses of pembrolizumab received and other baseline characteristics will also be explored as variables for safety and efficacy (eg, age, number of prior recurrences, baseline NANO and KPS, extent of prior resection, prior bevacizumab and chemotherapy use, tumor genetic profile).

All patients enrolled and treated with PVSRIPO will be summarized in all analyses. In addition, a per-protocol analysis will also explore the impact of excluding patients meeting pre-defined criteria from radiographic and survival analyses as outlined in [Section 8.4.6](#). For comparisons of efficacy or safety relative to PVSRIPO alone or pembrolizumab alone from other data sources, both the overall and per-protocol populations may be considered.

In general, patients should follow the protocol treatment plan outlined and will be considered on study if there are no major protocol deviations including prohibited tumor-treatments, until the time of confirmed disease progression, or until the investigator and/or patient feel it is in the patient's best interest to stop study treatments or study participation.

The SAP, which will be finalized before conducting the analyses, will present details about planned statistical summary methods and analyses. A brief summary of the SAP is provided below by section. The SAP will govern in the event the protocol and the SAP differ.

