#### **8.4.5 Safety Analysis**

The full safety analysis set will include all patients who were administered at least one dose of the PVSRIPO. The safety of study-required pre-infusion procedures including catheter placement, will also be summarized.

Separate summaries will be prepared for the primary safety analysis set, which is patients who received PVSRIPO and  $\geq 1$  dose of pembrolizumab. Patients who received PVSRIPO alone will be summarized separately (secondary safety analysis).

Summaries of TEAE will begin at the time of PVSRIPO infusion. Adverse events considered related to screening or other pre-infusion procedures that are not SOC (eg, PV booster, biopsy prior to infusion, catheter placement without PVSRIPO infusion) will be summarized separately (screening data set).

All safety endpoints for patients receiving PVSRIPO and  $\geq 1$  dose of pembrolizumab may be summarized overall and by the number of pembrolizumab treatments received while on study (eg, 1, 2 to 3, 4 to 6, etc.).

Adverse events will be summarized by highest grade per patient and by attribution according to CTCAE v5.0, using the latest version of MedDRA preferred term as event category and MedDRA primary system organ class body term as Body System category. Unless otherwise stated, adverse events will be displayed in terms of frequency tables by treatment group by decreasing frequency. Each patient will be counted only once within each preferred term or system organ class. If a patient experiences more than one AE (or laboratory value) within a preferred term or system organ class for the same recording period, only the AE with the strongest relationship or the worst severity, as appropriate, will be included in the summaries of relationship and severity.

Events meeting the criteria for a DLT or SAE, leading to discontinuation, resulting in death, etc., will be reported in additional summaries. Changes from baseline over time and abnormal laboratory values, vital signs and NANO and KPS will also be reported.

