Changes in toxicity grade, seriousness or outcome of AEs are recorded as separate entries in the eCRF with associated end and start dates (start date equals end date of previous entry). Such entries reporting the same event in such immediately consecutive periods will be considered as one event in the analysis in case of an improvement in toxicity grade. These events will be kept as separate records in the database to maintain the full detailed history of the events. The start date of the initial record in the sequence is taken as start date of the entire event. Duration of the AE will be adjusted accordingly in the analysis.

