#### Safety

- 14.3.1.1 Overall Summary of Treatment-Emergent Adverse Events, Safety Set
- 14.3.1.2 Treatment-Emergent Adverse Events by System Organ Class, Preferred Term, and Greatest Severity, Safety Set
- 14.3.1.3 Treatment-Emergent Adverse Events by Preferred Term in Descending Frequency, Safety Set
- 14.3.1.4 Treatment-Emergent Adverse Events Related to Study Drug or Catheter by System Organ Class, Preferred Term, and Greatest Severity, Safety Set
- 14.3.1.5 Treatment-Emergent Adverse Events Related to Study Drug or Catheter by Preferred Term in Descending Frequency, Safety Set
- 14.3.1.6 Treatment-Emergent Serious Adverse Events by System Organ Class, Preferred Term and Greatest Severity, Safety Set
- 14.3.1.7 Treatment-Emergent Serious Adverse Events Related to Study Drug or Catheter by System Organ Class, Preferred Term, and Greatest Severity, Safety Set
- 14.3.1.8 Treatment-Emergent Dose Limiting Toxicities by System Organ Class, Preferred Term and Greatest Severity, Safety Set
- 14.3.1.9 Treatment-Emergent Adverse Events of Special Interest for Lerapoltrev by System Organ Class, Preferred Term, and Greatest Severity, Safety Set
- 14.3.1.10 Treatment-Emergent irAEs for Pembrolizumab by System Organ Class, Preferred Term, and Greatest Severity, Safety Set
- 14.3.1.11 Treatment-Emergent Adverse Events Leading to Discontinuation of Study Treatment by System Organ Class, Preferred Term, and Greatest Severity, Safety Set
- 14.3.4.1 Summary of Grade Shifts in Laboratory Abnormalities – Hematology, Safety Set
- 14.3.4.2 Summary of Grade Shifts in Laboratory Abnormalities – Chemistry, Pancreatic and Thyroid, Safety Set

- 14.3.4.3 Number of Participants with at Least One ALT, AST, or Total Bilirubin Above Upper Limit of the Normal Range Post-Baseline, Safety Set
- 14.3.4.4 Summary of Vital Signs by Visit, Safety Set
- 14.3.4.5 Summary of Karnofsky Performance Status by Visit, Safety Set
- 14.3.4.6 Summary of Neurologic Assessment in Neuro-Oncology Score by Visit, Safety Set

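### SAP 5.8.1 lets a preferred term take its grade from one event and its relationship from another, so Tables 14.3.1.4 and 14.3.1.7 can show related Grade 3+ events that no record supports

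*SAP*

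**What the plan says.** SAP 5.8.1 sets the rule for a participant with several events under one PT: "the greatest severity and strongest assessment of relation to a study drug will be assigned to the PT for the appropriate summaries". It then plans summaries that use both attributes together: "The occurrence of TEAEs and TEAEs related to study drug or catheter will be summarized by PT, system organ class, and severity". The table list in SAP section 10 carries this out. Table 14.3.1.4 is titled "Treatment-Emergent Adverse Events Related to Study Drug or Catheter by System Organ Class, Preferred Term, and Greatest Severity, Safety Set", and Table 14.3.1.7 does the same for serious events. The overall summary (Table 14.3.1.1) also has rows that join grade and relationship, for example "Any Grade 5 TEAEs related to study drug or catheter with sub bullets for Grade 5 TEAEs related to catheter placement, lerapolturev or pembrolizumab".

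Protocol 8.4.5 has a different rule for the same situation: "only the AE with the strongest relationship or the worst severity, as appropriate, will be included in the summaries of relationship and severity". That rule selects one recorded event. SAP section 6, which lists the changes from the planned analyses, does not mention this one. Protocol section 8 settles precedence: "The SAP will govern in the event the protocol and the SAP differ".

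**The concern.** The SAP rule takes two maxima and attaches both to the PT. In a table of severity alone, or of relationship alone, this does no harm. In a table that crosses them, the grade can come from an unrelated event and the relationship from a mild one. The cell then reports a severe related event that nobody recorded.

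The setting makes such pairs plausible. Protocol 7.5.2 says that peritumoral and cerebral edema may arise from the tumor, surgery, earlier radiation or immune infiltration, and it lists seizure, headache and hemiparesis among the signs. One participant could therefore have the same PT twice with different attributions. SAP 3.2.3.1 adds another route: a missing severity becomes Grade 3, and a missing relationship becomes definite for events starting on or after catheter placement. Imputation could thus supply either half of a false pair.

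Frequency and severity of treatment-emergent events is a primary safety endpoint, and severe related events are the part readers look at first.

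**Working it through.** The documents state no figure for this rule, so there is none to reproduce. The check applies each rule to the same records.

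**Notation.** For one participant and one PT, record i has grade g_i and relationship r_i. The SAP gives no cut-off for related; I take possible or stronger as related. The first and last rows below do not depend on that choice.

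- SAP as written: grade = max(g_i) over all records; the PT is related if max(r_i) is related.
- Related records first: grade = max(g_i) over the related records only.
- Protocol 8.4.5, first selector: the single record with the worst severity.
- Protocol 8.4.5, second selector: the single record with the strongest relationship.

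| Records | SAP as written | Related first | Worst-severity record | Strongest-relationship record |
|---|---|---|---|---|
| G3 unrelated + G1 definite | related G3 | related G1 | G3, not related | related G1 |
| G4 unrelated + G1 possible | related G4 | related G1 | G4, not related | related G1 |
| G5 unrelated + G2 possible | related G5 | related G2 | G5, not related | related G2 |
| G3 definite + G1 unrelated | related G3 | related G3 | related G3 | related G3 |

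In the first three rows only the SAP wording yields a related severe event. Neither protocol selector does.

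**Direction.** The related records are a subset of all records, so their maximum grade cannot exceed the overall maximum. The SAP rule can raise a related grade but never lower it.

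**Which patterns are affected.** A false related Grade 3+ entry needs at least one related record, all related records below Grade 3, and at least one unrelated record at Grade 3 or above. With two records, grades 1 to 4, and related or unrelated, there are (4 × 2)² = 64 ordered combinations. The false pattern needs a related Grade 1 or 2 (2 choices), an unrelated Grade 3 or 4 (2 choices) and either order (2): 2 × 2 × 2 = 8 of 64. This counts patterns; it is not a frequency.

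**Size per affected participant.** One participant is 1/N of the cell: 1/30 = 3.3 percentage points, 1/20 = 5.0, 1/10 = 10.0. Thirty is the planned number. SAP section 6 says the full sample was not enrolled but gives no count, so 20 and 10 are assumptions. The tables use the Safety Set (everyone with a catheter placed), whose size is not given either.

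**The case against.** The best defense is the closing phrase of the SAP sentence, which limits the rule to the summaries where it fits. On that reading, severity tables take the greatest severity and relationship tables the strongest relationship. A programmer given the title of Table 14.3.1.4 could select related events first and then grade them, which is correct. This stands as a possible reading. It does not remove the problem, because both maxima fit a crossed table and no sentence tells the programmer to select first. Two programmers could follow the text and produce different related Grade 3+ counts.

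Other points on that side also stand:

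- The protocol rule does not say which of its two selectors applies in a crossed table. It is incomplete too, but neither selector invents an event.
- The overall rows for related Grade ≥3 and Grade 5 are worded at event level, so they may never pass through the PT rule. The clear exposure is in Tables 14.3.1.4 and 14.3.1.7.
- Reporting rules limit mixed pairs. Protocol 7.1 asks for the diagnosis where known, 7.5.2 puts edema symptoms on dedicated forms, 7.1.3 ends collection 30 days after a participant leaves the study, and 7.2 does not count death from progression as an adverse event.
- The error overstates harm, and every event is listed, so a suspect cell can be checked by hand.

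Three stronger inferences are tempting. First, Protocol 8.4.5 says "Changes in toxicity grade, seriousness or outcome of AEs are recorded as separate entries in the eCRF", from which a reader might conclude that mixed pairs are routine. That sentence concerns changes within one event and says nothing of attribution. Second, a reader might assume event probabilities and derive an inflated related Grade 3+ rate. The documents supply none of those inputs, so the result would only restate the assumptions. Third, a reader might expect the rate to be set against the Phase 1 dose-expansion figure, "19% of patients had a PVSRIPO-related AE of grade 3 or higher". The protocol allows informal comparisons with other data sources; no formal comparison with that figure is planned.

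**Conclusion.** The concern holds as a defect in the stated rule. Applied literally in Tables 14.3.1.4 and 14.3.1.7, SAP 5.8.1 turns an unrelated Grade 3+ event plus a lower-grade related event of the same PT into a related Grade 3+ event that did not occur. It departs from the protocol without being logged, and the SAP text governs.

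The total effect cannot be estimated from the documents. Per affected participant it is 3.3 percentage points on that PT's cell at a denominator of 30, and more at a smaller one. The bias is upward only. The conclusion rests on the literal reading; if related records are in fact selected first, the tables are right and only the wording is at fault. Severity-only tables, relationship-only tables and the adverse event listing are unaffected. Whether the overall rows are affected cannot be told from the text.

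**What to change.** Replace the sentence in SAP 5.8.1 with:

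> For tables of related events, first select TEAE records assessed as related to the product (or catheter) in question, then take the greatest severity among those records within participant and PT. For tables of all TEAEs, take the greatest severity regardless of relationship.

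For the pooled Tables 14.3.1.4 and 14.3.1.7, the first step selects records related to any of catheter placement, lerapolturev or pembrolizumab. State also that the related Grade ≥3 and related Grade 5 rows of Table 14.3.1.1, with their sub-rows, count participants who have at least one single event meeting both conditions. This also prevents a grade attributed to one agent from appearing under another.

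Record the departure from Protocol 8.4.5 in SAP section 6. An entry is needed even after the fix: for a possible Grade 3 plus a definite Grade 1 event, the new rule gives related Grade 3 (with possible counted as related), while the protocol's strongest-relationship selector gives Grade 1.

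The cost is two sentences, one log entry and a change in the order of two programming steps. No new data are needed. If the tables already exist, compare each related Grade 3+ cell with Listing 16.2.7.1.
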